### **5.3 Participant Recruitment**

We anticipate recruiting 750 participants from CTU studies that meet the above criteria. We anticipate none of the CTU participants will be excluded from the ANNE Vital Sign System assessment based on the exclusions in section 5.2.

### **5.4 Participant Withdrawal and Discontinuation of IP**

#### ***5.4.1 Reasons for Withdrawal/Discontinuation of IP***

Participants can choose to end their participation in this research (called withdrawal) at any time without having to provide a reason. If participants choose to withdraw from the study, they are encouraged to contact the study doctor or study staff.

Information that was recorded before participant withdrew will be used by the researchers for the purposes of the study, but no information will be collected after withdrawal of participant permission. If participant would like information that was recorded before they withdrew not to be used by the researchers, they may submit a verbal or written request to the study staff and their data will not be used.

The study doctor may stop their participation in the study early, and without their consent, for reasons such as:

- Participant is unable to complete all required study procedures
- The study doctor no longer feels this is the best option for the participant

- The Sponsor decides to stop the study
- The Regulatory Authority/ies (for example, Health Canada) or research ethics board withdraw permission for this study to continue

If participant is removed from this study, the study doctor will discuss the reasons with them.

#### **5.4.2 Data Collection and Follow-up for Withdrawn Participants**

Participants withdrawing from the study should be contacted by the study research team for follow up assessment or to follow up with any unresolved adverse events. Once withdrawn from the study, no further study procedures or evaluations should be performed, or additional study data collected. However, every effort should be made to obtain permission to document the reason for withdrawal and to collect participant outcomes, such as survival data up to the protocol-described end of participant follow up period, where possible. Any data collected prior to the withdrawal of consent may be retained and used by the sponsor and may be used in analysis towards the aims of this study. Participants will be required to return all study devices and associated equipment and materials at the time of withdrawal.

## 6 INTERVENTIONS

### 6.1 Investigational Product

The ANNE Vital Sign System was originally created for the purposes of providing real-time vital signs monitoring in the paediatric intensive care unit. The ANNE Vital Sign System consists of two water-resistant sensors, each encapsulated with a biocompatible silicone material. The ANNE Chest has two exposed gold-plated electrodes, but there are no external wires extending from the Sensor. The Sensor measures biosignals including electrocardiogram (ECG), acceleration, and temperature to measure vital signs such as heart rate, respiratory rate, body temperature, and skin temperature. The ANNE Limb is fully enclosed by the silicone encapsulation and measures photoplethysmogram for pulse rate, SpO2, body temperature, and skin temperature measurements

#### **6.1.1 Acquisition, Formulation and Packaging**

##### **6.1.1.1 Acquisition and Formulation**

53 ANNE Vital Sign System sensor sets will be shipped directly to Sunnybrook Research Institute from the manufacturer (Sibel Inc., Evanston, IL).

##### **6.1.1.2 Packaging**

ANNE Vital Sign System sensor sets will be shipped as a bulk order with all units individually boxed.

#### **6.1.2 Receiving, Storage, Dispensing and Return**

##### **6.1.2.1 Receipt of Investigational Product**

Upon receipt of the investigational product and/or study supplies, an inventory must be performed and a receipt log filled out and signed by the research team member accepting the shipment. It is important that the designated study staff counts and verifies that the shipment contains all the items noted in the shipment inventory. Any damaged or unusable product in a given shipment will be documented in the study files. The site must notify the study sponsor of any damaged or unusable product that was supplied to the site.

##### **6.1.2.2 Storage and Stability**

The sensors may be stored at room temperature.

##### **6.1.2.3 Dispensing of Investigational Product**

The investigational product will be reconciled by the research team at regular intervals, in addition to reconciliations performed during monitoring. Reconciliation will include verification of

investigational product kit/device assignment, inventory and recording of any damage or markings on the investigational product.

#### **6.1.2.4 Return and/or Destruction of Investigational Product**

At the completion of the study, there will be a final reconciliation of investigational product shipped, used, returned, and remaining. This reconciliation will be documented. Any discrepancies noted will be investigated, resolved, and documented prior to return of the devices to the manufacturer.

## 7 STUDY SCHEDULE AND PROCEDURES

### 7.1 Screening

At the time of their enrollment in CTU and affiliated studies at participating recruitment sites, individuals will be invited to indicate interest in participating in the ANNE Vital Sign System assessment. This will be done by secure video conference. If interested, participant contact information (name, telephone number, email address) and study ID will be sent by encrypted email to study staff at SRI. Study staff at SRI will confirm that there are no exclusions from the ANNE Vital Sign System assessment based on exclusion criteria specific to the ANNE Vital Sign System. Eligible participants will be asked to complete a separate informed consent process specific to the ANNE Vital Sign System study. For participants enrolled at French-speaking sites, a study team member from that site may assist SRI with participant communications.

For the purposes of this study, the consent process will be completed remotely. A site team member will email a copy of the consent form to the participant and schedule a phone/video call with the participant where they will walk through the key elements of consent with the participant and allow time for questions. If a participant is unable to receive the consent form, they will be mailed a hard copy. After walking through the key elements of consent and the participant has been given time and opportunity to consider participation and ask questions, they will be asked their willingness to participate. If agreeable, study staff and witness will sign and date two copies of the consent form, to be included in the shipment of study device and materials. For those who indicate a desire to participate, study staff will collect mailing information (name, address). Study staff will explain the mailing procedures and tell the participant to expect a package in the mail with tracking information emailed to them. This package will include two hard copies of the consent form, already signed by study staff and witness.

A second scheduled phone/video call with the participant will be conducted after the participant has received the package. During this call, key elements of the consent form will be reviewed again and participants will have additional opportunity to ask questions. If agreeable, participants will then sign both copies of the consent form, retain one for their records, and return the other in the return package with the device after completion of their measurements.

The method of obtaining and documenting the informed consent and the contents of the consent must comply with ICH-GCP and all applicable regulatory requirement(s).

It will be made clear to each potential participant or substitute-decision maker, that informed consent may be withdrawn at any time without needing to give a reason and that such withdrawal will not compromise the relationship between the participant and the Investigator nor the participant's future treatment.

The ICF must be in a language fully comprehensible to the prospective participants and ample opportunity must be given to inquire about the details of the study.

The ICF will include consent to access stored data for future analyses.

## **7.2 Baseline/Enrollment**

Participants who are confirmed eligible and enrolled in CTU, are not excluded based on exclusion criteria specific to the ANNE Vital Sign System, and have completed the informed consent process will be provided instruction for use via video-conference with a member of the study team.

Study device will be sent to the participant via pre-paid package and tracked by a member of the study team.

As soon as possible after the study device and materials are received by the participant, study staff will instruct the participant on the proper application and use of the ANNE Vital Sign System via remote video-conference. Specifically, study staff will instruct the participant to affix the ANNE Vital Sign System chest sensor to the participant's chest using electrode paste, ANNE chest adhesive and Tegaderm or similar. Study staff may ask participants to shave a 3"x2" section of their chest, but participants will be informed this is optional. Next, study staff will instruct the participant to affix the ANNE Vital Sign System finger sensor to the participant's non-dominant index finger using the ANNE limb adhesive. Participants will wear the sensors for 24 hours before removing it themselves at home. Within 24 hours of removing the device, participants will be asked to fill out the Feedback Survey of Device Experience (Appendix 1), noted as optional. Finally, participants will be asked to return the device and feedback form by shipping back to SRI using a pre-paid, pre-addressed package. A new device and feedback form will be shipped to participants for their 12 month visit.

## **7.3 Study visits/Follow up**

Baseline procedures will be repeated 12 months later. Participants at either time point with an AHI of  $\geq 15$  as determined by our quantification will be called via telephone by study staff to be a) notified that they have a high probability of having sleep apnea and if accompanied by severe sleepiness should refrain from driving, b) encouraged to contact their family physician for clinical evaluation where an official diagnosis of sleep apnea may or may not be made, and c) asked to notify study staff if they obtain treatment, unless treatment is obtained after their month 12 visit. Participants will be reminded that data collected as part of this study are for research purposes only and may not constitute a diagnosis of sleep apnea.

## **7.4 Protocol Deviations**

It is the responsibility of the investigator to ensure that only investigative procedures, as outlined in this protocol are performed on study participants; the occurrence of deviations from the protocol or standard operating procedures (SOP) are limited; and compliance with the regulations is maintained. Planned deviations from the protocol must not be implemented without prior agreement from the sponsor and approval from the local REB, as required, unless to eliminate an immediate hazard to a participant.

Planned or unplanned deviations may occur on the part of the participant, the investigator, or study research team. In resolution to a deviation, corrective/preventative actions are to be

developed and implemented in a timely manner. Protocol deviations will be documented and reported as required and assessed where necessary during analysis.

## **8 ASSESSMENT OF SAFETY**

The safety of research participants is foremost and should always be considered throughout the conduct of research.

### **8.1 Definitions**

#### **8.1.1 Adverse Events**

An adverse event (AE) means any untoward medical occurrence in a participant from the time of first contact with the ANNE Vital Sign System to 7 days following removal of the ANNE Vital Sign System at both Baseline and at Month 12. Participants will be advised during the informed consent process that it is their responsibility to report any adverse events to study staff up to seven (7) days following removal of the ANNE Vital Sign System sensors. Participants will be given the contact information of two CPSO-licensed physicians serving as qualified investigator and co-investigator. In the unlikely event that a participant experiences a possible adverse event, the qualified investigator or co-investigator will 1) advise the patient to seek care with their local health care provider, 2) liaise with the local health care provider, with the consent of the participant, to support the provision of necessary health care; and 3) collect information on, record, and report as necessary to the REB and Health Canada details of the possible adverse event.

An AE can therefore be any unfavorable and unintended sign (including an abnormal laboratory finding, for example), symptom, or disease temporally associated with the use of the investigational product, whether or not considered related to the investigational product.

#### **8.1.2 Serious Adverse Events**

A serious adverse event (SAE) or reaction is any untoward occurrence that:

- Results in death,
- Is life-threatening,
- Requires inpatient hospitalization or prolongation of existing hospitalization,
- Results in persistent or in significant disability/incapacity,
- Is a congenital abnormality or a birth defect.

The term "life-threatening" in the definition of "serious" refers to an event in which the participant was at risk of death at the time of the event; it does not refer to an event which hypothetically might have caused death if it were more severe.

#### **8.1.3 Unexpected Adverse Event**

An unexpected adverse event is any AE that is not identified in nature, severity or frequency in the current Investigator's Brochure or Product Monograph.

### **8.2 Assessment of an Adverse Event**

### **8.2.1 Relationship (Causality/Relatedness)**

The causality assessment is the determination, according to the investigator's clinical judgment, of the existence of a reasonable possibility that the investigational device caused or contributed to an adverse event.

If the investigator or delegated sub-investigator is unsure about whether or not the investigational device caused or is related to the event, then the event will be handled as "related" to the investigational device for reporting purposes of the trial. If the causality assessment is "unknown but not related" to the investigational device, this should be clearly documented in the source documents.

### **8.2.2 Expectedness**

Events are classified as unforeseen or unexpected if the nature, severity or frequency is not consistent with the risk information set out in the Product Monograph (PM) or label.

### **8.2.3 Seriousness**

Events are classified as serious if associated with effects threatening the life or physiological functions of a participant. Refer to the definition for "Serious Adverse Events" in section 8.1.2.

### **8.2.4 Severity**

The term "severe" is often used to describe the intensity (severity) of a specific event (e.g. mild, moderate, or severe myocardial infarction); the event itself, however, may be of relatively minor medical significance (such as severe headache). This is not the same as "serious," which is based on participant/event outcome or action criteria usually associated with events that pose a threat to a participant's life or functioning. The terms "serious" and "severe" are not synonymous. Seriousness (not severity) serves as a guide for defining regulatory reporting obligations.

## **8.3 Adverse Event Recording**

All AEs both non-serious and either temporally and causally related to study procedures (i.e., a new event or an exacerbation of a pre-existing condition) that occur from the time of first contact with the ANNE Vital Sign System to 7 days following removal of the ANNE Vital Sign System at both Baseline and at Month 12 will be recorded as an AR in LORIS.

The following are not considered AEs and therefore do not require recording:

- Pre-existing diseases or conditions identified and recorded at screening/baseline unless, at the discretion of the investigator, the disease or condition worsens in severity or frequency

- At the discretion of the investigator, events considered likely manifestations of the underlying disease or that commonly occur in the study population independent of exposure to the investigational device
- Elective medical or surgical procedures.

Details of the event must include the dates of onset and resolution, severity, relationship to study procedures, seriousness, whether the event caused the participant to withdraw from the study, and outcome.

**Severity:** Severity should be graded and recorded according to the table below.

Severity	Definition
Mild	Awareness of event but easily tolerated
Moderate	Discomfort enough to cause interference with usual activity
Severe	Inability to carry out usual activity, incapacitating, requires medical intervention

**Relationship:** The relationship of the AE to study procedures will be determined by the Investigator, and assessed using the following definitions:

Relationship	Description
Not Related	There is no evidence of a causal relationship and a causal relationship cannot be reasonably attributed to the study procedures. The event is clearly due to non-study causes.
Unlikely Related	A poor temporal relationship exists between the event onset and study procedures. The event could easily be explained by the participant's clinical state, intercurrent illness, or concomitant therapies.
Possibly Related	A relationship between event onset and study procedures cannot be ruled out with certainty and the event may be related. There is some evidence to suggest a causal relationship but the influence of other factors may have contributed to the event, such as the participant's clinical condition or concomitant treatment.
Probably Related	The event is likely related to study participation. There is evidence to suggest a causal relationship, such as reasonable temporal sequence from procedure. The influence of other factors is unlikely.
Definitely Related	The event is clearly related to study participation. There is clear evidence to suggest a causal relationship. The influence of other factors can be ruled out.

These criteria, in addition to good clinical judgment, should be used as a guide for determining the causal assessment.

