### **8.5 Type and Duration of Follow-up for Adverse Events**

AEs occurring as of the first contact of the investigational product and 7 days following removal of the investigational product will be collected. AEs recorded during this period will be followed through to resolution, or until the event is assessed as chronic or stable. If an AE remains unresolved at the conclusion of participation, the Investigator will make a clinical assessment to determine whether continued follow-up of the AE is warranted.

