## **8.6 Reporting and Entry Timelines**

Study investigators will report SAEs to the sponsor within the following timelines:

- All deaths and immediately life-threatening events, whether related or unrelated, will be recorded and reported to the sponsor within 24 hours of site awareness.
- Serious adverse events other than death and immediately life-threatening events, regardless of relationship, will be reported to the sponsor within 72 hours of site awareness.

Adverse event information will be entered into the CRF in a timely manner and **no later than 15 days** from the time the investigator becomes aware of the event.

Serious adverse event information will be entered into the CRF in a timely manner/**within 72 hours** from the time the investigator becomes aware of the event.

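### The opening sentence of section 8.3 is garbled and, read literally, records fewer adverse events than sections 8.1.1 and 8.5 call for, so non-serious events could go unrecorded

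*Combined protocol and SAP*

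**What the plan says.** Section 8.1.1 defines an adverse event broadly. It covers any unfavourable medical happening from first contact with the device until 7 days after it is taken off, at Baseline and at Month 12, "whether or not considered related to the investigational product". Section 8.5 matches that scope: "AEs occurring as of the first contact of the investigational product and 7 days following removal of the investigational product will be collected".

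Section 8.3 is the recording rule. Its opening sentence covers "All AEs both non-serious and either temporally and causally related to study procedures" in the same window and says these "will be recorded as an AR in LORIS". It then lists what does not count as an adverse event and so need not be recorded. One item, left to the investigator's discretion, is "events considered likely manifestations of the underlying disease or that commonly occur in the study population independent of exposure to the investigational device". For each recorded event, the required details include "severity, relationship to study procedures, seriousness, whether the event caused the participant to withdraw from the study, and outcome". The relationship scale has five grades, the first two being *Not Related* and *Unlikely Related*.

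Serious events have further provisions. Section 8.4.1 has them recorded and reported to the REB. Section 8.6 sets 24-hour and 72-hour deadlines for reporting them to the sponsor, whatever the relationship, and adds: "Serious adverse event information will be entered into the CRF in a timely manner", with a 72-hour limit. Section 8.6 also gives a 15-day limit for entering adverse-event information in the CRF, with no condition on relatedness.

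**The concern.** A recording rule should be at least as wide as the definition it serves. Here the definition includes unrelated events, and the rule, on its face, does not. The common-event clause raises a second problem. It asks the investigator to decide that an event is independent of the device before the event is written down, whereas 8.1.1 makes relatedness irrelevant to whether something is an adverse event.

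What is at stake is the completeness and consistency of the safety record for an investigational device that participants apply to themselves at home. Stopping rule (1) in section 10.4 asks whether adverse events call the safety of the intervention into question. Sections 8.1.3 and 8.2.2 define an unexpected event partly by its frequency. An excess of a common complaint such as mild skin irritation is hard to see if single cases can be dismissed as common before they are entered.

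**Working it through.** The plan states no figure on this point and no formula applies. The check compares the sections.

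1. **Grammar of the opening sentence of 8.3.** The word *both* introduces only one term (non-serious), and *either* is followed by *and*. At least one word is missing or wrong, and the intended wording appears nowhere else in the document.

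2. **What each possible reading would put in LORIS.** Take four kinds of event in the window: (a) non-serious and related, (b) non-serious and unrelated, (c) serious and related, (d) serious and unrelated.
   - As written: (a) only.
   - If *serious* was dropped but *and* is right: (a) and (c).
   - If *and* should be *or* but the limit to non-serious events stands: (a) and (b), because any event in the window is related in time.
   - If both slips are repaired: all four.

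3. **8.3 against 8.1.1.** Section 8.1.1 makes all four kinds adverse events. The literal rule leaves out three of them, so the conflict is direct.

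4. **8.3 against 8.5.** Section 8.5 collects adverse events in the window with no limit by seriousness or relationship. The literal opening of 8.3 conflicts with that. The common-event clause does not independently conflict with 8.5, because 8.5 speaks of AEs and the clause says what is not one. That conflict is with the definition in 8.1.1.

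5. **8.3 against itself.** If only non-serious, related events were entered, the seriousness field could take one value, and 2 of the 5 relationship grades would never be used. A form that asks for both items expects both to vary.

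6. **8.3 against 8.4.1 and 8.6.** Kinds (c) and (d) must be recorded or reported under these sections, and 8.6 requires CRF entry. They can be read as a separate route for serious events, so they need not contradict 8.3. Kind (b) has no such route of its own. Only the general 15-day CRF line in 8.6 applies, and whether a given event counts as an AE leads back to 8.1.1 or 8.3.

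7. **Common-event clause against 8.2.1.** Section 8.2.1 treats uncertain causality as related for reporting. If an event is set aside as independent of the device before it is recorded, that default may never be applied.

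8. **Terminology.** AR, the label for the LORIS entry, is not in the list of abbreviations.

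9. **Exposure.** 750 participants × 2 wear periods = 1,500 periods at most, assuming full enrolment and no dropout. Each is observed for about 8 days (24 hours plus 7 days). This counts observation time, not missed events.

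**The case against.** The strongest reply is that this is a drafting slip and not a decision. The seriousness field and the two unrelated grades suggest that the authors meant to record everything, and if *or* was intended the restriction nearly vanishes. That is a fair inference, and it rules out saying that the plan has chosen to exclude unrelated events. It does not cure the text, because staff must work from the sentence as printed and could read it differently.

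A reader might infer that serious events are lost. The documents do not support that: sections 8.4.1, 8.4.2 and 8.6 have them recorded, reported and entered in the CRF, and 8.6 applies regardless of relationship. A reader might also infer that regulatory reporting is compromised. Section 8.4.3 ties reporting to Health Canada to a device incident reaching the qualified investigator's attention, not to an entry under 8.3. Nor is 1,500 wear periods a measure of harm.

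Other points on this side also stand. The common-event clause is limited to events independent of device exposure. Stopping rule (1) is qualitative and names no LORIS listing. Section 2.4 calls the study minimal risk, and sections 2.3 and 2.4 report no adverse events in earlier device use. These points lower the stakes. They do not remove the conflict with 8.1.1, and the drafting-slip explanation does not reach the common-event clause, which is grammatical and deliberate.

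**Conclusion.** The point holds as a wording and consistency fault. The opening of 8.3 is ambiguous and, taken literally, contradicts 8.1.1, 8.5 and 8.3's own fields. The common-event clause places attribution ahead of recording, contrary to 8.1.1. The consequence is that non-serious events judged unrelated or common could go unrecorded, or be recorded by some staff and not by others, which would weaken the record that stopping rule (1) would draw on. The word is *could*: the effect depends on how staff read the sentence and use their discretion. Its size cannot be given, since the documents state no event rate. The primary analysis of cognitive change is not affected. The sponsor should correct this, and preferably early, because unrecorded minor events may be hard to recover later.

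**What to change.** Replace the opening sentence of 8.3 with text to this effect: *All AEs, serious and non-serious, that begin between first contact with the device and 7 days after its removal, at Baseline and at Month 12, are entered in LORIS regardless of relationship, and are then graded for severity, seriousness and relationship.*

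Reconcile the common-event clause with 8.1.1 so that attribution is graded after the event is recorded. Deleting the clause is one way, but whether to delete or narrow it is partly a matter of preference. Unchanged pre-existing conditions are already covered by the first item in the same list. Add a cross-reference from 8.3 to 8.6 for the serious-event timelines, and define AR or correct it. Sections 8.1.1 and 8.5 already have the wider scope and 8.6 sets timelines, so the new sentence need not be repeated there.

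The cost is a wording amendment, which needs REB review under section 13.2, and a few more minor events to enter.
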